4. STUDY PERIODS, TREATMENT REGIMENS, AND POPULATIONS FOR ANALYSIS

4.1. Study Periods for Analyses

Study periods are defined in Table 2.

Table 2. Definition of Study Periods for Analysis

Period	Definition
Baseline / Screening	From the day of Informed consent form (ICF) signature (up to 28 days before first dose) to the day and time of the first dose of study drug.
On-treatment	From the date of first dose of study drug through 30 days after the last dose of study drug. Unless otherwise specified, the on-treatment period will be the basis for the summaries of safety.

4.2. Treatment Groups/Cohorts

There are two cohorts in this study as described in Section 3.1. Patients in Cohort A must have an *FGFR3* mutation or *FGFR1-4* fusion/rearrangement. All other patients with UC (including patients with other *FGFR* or non-*FGFR* genetic aberrations and patients with wild-type [non-mutated] tumors) will be included in Cohort B.

4.3. Populations for Analysis

- **All Enrolled Population:** All patients enrolled in this study
- **All Treated Population/Full Analysis Set:** All patients in the All Enrolled Population who received at least one dose of study drug. Unless otherwise specified, the All Treated Population will be the basis for the summaries of efficacy and safety.

■ CCI

4.4. Timing of Analysis

The final analysis for the primary objective will be performed when all patients 1) discontinue study treatment, or 2) have at least 6 months follow-up.

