3.2.3. Post-Discontinuation Considerations

Patients who discontinue without documented disease progression should continue to undergo tumor assessments according to the Schedule of Events (that is, every 9 weeks ± 7 days) until progressive disease (PD) is documented, new anticancer therapy is initiated, the study is terminated, or the patient dies, withdraws consent, or is lost to follow-up).

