8.1.4. Objective Response Assessment

Assessments will be based on the definitions provided in [Table 12](#) and [Table 13](#). Since this is a non-randomized study, all responses (CR/PR) must be confirmed.

Table 12: Time Point Response for Patients with Target (\pm Non-target) Disease

Target Lesions	Non-Target Lesions	New Lesions	Objective Response
CR	CR	No	CR
CR	Non-CR/Non-PD or Not all evaluated	No	PR
PR	Non-PD or Not all evaluated	No	PR
SD	Non-PD or Not all evaluated	No	SD
Not all evaluated	Non-PD	No	NE
PD	Any	Yes or No	PD
Any	PD	Yes or No	PD
Any	Any	Yes	PD

Table 13: Time Point Response for Patients with Only Non-target Disease

Non-Target Lesions	New Lesions	Objective Response
CR	No	CR
Non-CR/Non-PD	No	SD
Not all evaluated	No	NE
Unequivocal PD	Yes or No	PD
Any	Yes	PD

Abbreviations: CR=complete response; NE=not evaluable; PD=progressive disease; PR=partial response; SD=stable disease

The efficacy evaluation criteria described above will be used to derive the primary and secondary efficacy endpoints as defined in [Section 2](#).

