3. STUDY DESCRIPTION

3.1. Summary of Study Design

Study TAS-120-203 is an open-label, non-randomized, multicenter Phase 2 study evaluating the combination of futibatinib and pembrolizumab in patients with advanced or metastatic UC who are not candidates to receive a platinum-based treatment regimen. The design is briefly summarized in Figure 1.

Abbreviations: FGFR=fibroblast growth factor receptor; I.V.=intravenous; mg=milligrams; PD=progressive disease; PO=oral; QD=daily; Q3W=every 3 weeks; Tx=treatment.

Figure 1: Study design flow chart

A treatment cycle is defined as 21 days. All enrolled patients will receive the same treatment regimen:

- Futibatinib at an oral (PO) dose of 20 mg daily (QD); and
- Pembrolizumab at an intravenous (I.V.) dose of 200 mg every 3 weeks (Q3W).

Treatment will continue until disease progression, unacceptable toxicity, or any other of the criteria for treatment discontinuation is met; of note, pembrolizumab may be administered for a maximum of 35 doses or a maximum duration of 2 years, whichever is earlier.

The study will begin with a safety lead-in period. During this period, a total of 6 patients with advanced or metastatic urothelial carcinoma will be enrolled and treated for at least one 21-day cycle. Patients will be enrolled into this initial safety lead-in period without regard for FGFR alteration status.

After the first 6 patients have completed one cycle of treatment, the first safety analysis will occur. After confirmation of the safety of the combination, a total of 20 additional patients will be enrolled into each of the following 2 cohorts:

- Cohort A: Patients with UC and *FGFR3* mutation or *FGFR* fusion/rearrangement. Patients will be enrolled based on local results but tissue samples will be archived for retrospective confirmation at a central lab using next generation sequencing (NGS)
- Cohort B: All other patients with UC (including patients with other *FGFR* or non-*FGFR* aberrations and patients with wild-type [non-mutated] tumors)

A second safety analysis will occur after enrollment of a total of 10 patients (including the 6 patients from the safety lead-in), in order to confirm the safety profile of the combination before proceeding to the enrollment of the remaining patients in Cohorts A and B.

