Evaluation	Screening (Within 28 days of 1 st dose)	Treatment Period (1 cycle =21 days)					Safety Follow-up		Notes	
		Cycle 1		Cycle ≥2						
		D1 (-1 day)	D8 (-1 day)	D15 (-1 day)	D1 (-1 day)	End of Cycle (±7days)	End of Treatment (+0-7 days)	30, 60, and 90 days after last dose (±3 days)		
Hematology	X	X	X	X	X		X	X	Within 24 hours prior to dosing. More frequent assessments may be performed if clinically indicated	
Coagulation	X	X			X		X	X		
Chemistry (serum or plasma)	X	X	X	X	X		X	X		
Thyroid Function Tests	X	X			X				Every 6 weeks until discontinuation of pembrolizumab.	
Pregnancy test	X						X		Serum pregnancy test required within 7 days prior to first dose for WOCBP. Additional testing (urine or serum) as required per local practice.	
Ophthalmological examination	X			See Note					Examination to be performed by an ophthalmologist or qualified delegate. At screening, 4-6 weeks after first dose, and as indicated if symptoms or signs of mineral deposits. In cases of retinal pigment epithelial detachment, events should be monitored at 2-3-week intervals.	
CCI				X					CCI	

Evaluation	Screening (Within 28 days of 1 st dose)	Treatment Period (1 cycle =21 days)					Safety Follow-up		Notes	
		Cycle 1		Cycle ≥2						
		D1 (-1 day)	D8 (-1 day)	D15 (-1 day)	D1 (-1 day)	End of Cycle (±7days)	End of Treatment (+0-7 days)	30, 60, and 90 days after last dose (±3 days)		
Blood sample for CCI assessment		X			X		X		CCI [REDACTED]	
Tumor tissue collection for CCI assessment	X				X				Mandatory tissue collection at baseline (archival or new tumor biopsy). Optional tumor biopsy to be performed at Day 1 of Cycle 2 only .	
Tumor assessments (CT/MRI)	X					(X)	X	X	At baseline and the end of every 3 cycles (±7 days), or as clinically indicated, until radiologic PD or initiation of new anticancer therapy (whichever comes first). For patients who discontinue treatment for reasons other than radiographic disease progression, imaging will be performed at EOT, (if the prior scan was performed ≥9 weeks before EOT) and during Survival Follow-up until radiologic disease progression or initiation of new anticancer therapy (whichever occurs first).	
Survival status								X	For all patients, unless patient withdraws consent or the study is terminated early by the Sponsor.	

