5.4.1. Primary Efficacy Analyses

The primary endpoint is ORR per RECIST 1.1. The description of each efficacy endpoint is provided in Table 3. Tumor assessments will be performed as per Table 1. The evaluation of endpoints will be based on the Investigator or local radiologist.

Table 3. Efficacy Endpoint Definitions

Endpoint	Definition
ORR	The proportion of patients experiencing a best overall response of PR or CR
DCR	the proportion of patients experiencing a best overall response of SD, PR, or CR
DoR	The time from the first documentation of response (CR or PR) to the first documentation of objective tumor progression or death due to any cause, whichever occurs first
PFS	The time from first dose of study therapy to the date of death (any cause) or disease progression, whichever occurs first
OS	The time from the date of first dose to the death date

Abbreviations: ORR=objective response rate; CR=complete response; PR=partial response; SD=stable disease; DCR=disease control rate; DoR=duration of response; OS=overall survival; PFS=progression-free survival

ORR per RECIST 1.1 will be summarized by a binomial response rate for each cohort. ORR per RECIST 1.1 will be calculated based on the best overall response recorded from the start of treatment until progression disease or start of subsequent new anticancer treatment. The overall

response can be derived based on target lesion response, non-target lesion response and the emergence of new lesion for patients with measurable disease at baseline. Table 4 presents the rules to derive the overall response.

The best overall response, CR and PR, will be confirmed with at least 4 weeks intervals of two consecutive time points. A minimum of 6-week interval between initial treatment (first dosing date) and tumor measurement is required for SD. The confirmation rule of the best overall response per RECIST 1.1 is shown in Table 5.

The exact 2-sided 90% CI based on Clopper–Pearson methodology will be derived for ORR.

For Cohort A, the null hypothesis (ORR of 35%) will be rejected if at least 12 responders observed out of 20 patients.

For Cohort B, the null hypothesis (ORR of 25%) will be rejected if at least 9 responders observed out of 20 patients.

Table 4. Overall Response Assessment with Target/Non-target Lesion and New Lesions

Target Lesions	Non-target Lesions	New Lesions	Overall Response
CR	CR	No	CR
CR	Non-CR/Non-PD or Not all evaluated	No	PR
PR	Non-PD or Not all evaluated	No	PR

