SD	Non-PD or Not all evaluated	No	SD
Not all evaluated	Non-PD	No	Not evaluable
PD	Any	Yes or No	PD
Any	PD	Yes or No	PD
Any	Any	Yes	PD

Table 5. Confirmation Rules for Overall Response of PR and CR per RECIST 1.1

Earlier Response (to be confirmed)	Later Response (confirmation)	Confirmed Response
CR	CR	CR
CR	Not CR or missing	SD
PR	CR or PR	PR
PR	SD or PD or missing	SD
PR	SD and then PR (only one SD in between)	PR
SD	n/a – no confirmation needed	SD
PD	n/a – no confirmation needed	PD

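### The 6-month trigger for the primary ORR analysis falls just before the third scheduled scan, so responses still awaiting confirmation in the last-enrolled patients would usually be scored as stable disease

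*SAP*

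**What the plan says.** - **Trigger.** SAP 4.4: the final analysis of the primary objective "will be performed when all patients 1) discontinue study treatment, or 2) have at least 6 months follow-up". It does not say whether follow-up starts at consent, enrolment or first dose.
- **Scan calendar.** SAP 3.1: "A treatment cycle is defined as 21 days". The tumor-assessment row of SAP Table 1 sets scans "At baseline and the end of every 3 cycles (±7 days", and Protocol 3.2.3 describes the same schedule as "tumor assessments according to the Schedule of Events (that is, every 9 weeks". The Table 1 note also permits scans outside the schedule: "7 days), or as clinically indicated, until radiologic PD or initiation of new anticancer therapy (whichever comes first".
- **Confirmation.** Protocol 8.1.4: "Since this is a non-randomized study, all responses (CR/PR) must be confirmed". SAP 5.4.1: "CR and PR, will be confirmed with at least 4 weeks intervals of two consecutive time points".
- **Missing confirmation.** In SAP Table 5, a PR followed by "SD or PD or missing" becomes SD. A CR with no later assessment also becomes SD.
- **Patients off treatment.** Those without progression stay on 9-weekly scans (Protocol 3.2.3), but the end-of-treatment scan is done only if the previous one is at least 9 weeks old (SAP Table 1).
- **Not provided.** No scan is scheduled to confirm a response. The only planned 4-to-8-week repeat scan confirms progression under iRECIST (Protocol 8.2). No rule delays the data cut for a confirmation still due.

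**The concern.** ORR with mandatory confirmation needs two scans per responder, yet the cut-off is tied to elapsed months or treatment status and not to the scan calendar. Where the second scan falls after the cut, Table 5 turns a true response into SD, and the patient stays in the denominator as a non-responder. The loss comes from the calendar and not from the drug, and it falls on the last patients enrolled.

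The decision rules are fixed counts (12 of 20 in Cohort A, 9 of 20 in Cohort B, SAP 5.4.1), so in a borderline cohort a single unconfirmed responder can change the conclusion.

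**Working it through.** **Starting point.** For the SAP 5.4.1 rules, exact binomial power is P(X ≥ 12 | n = 20, p = 0.65) = 76.2% in Cohort A and P(X ≥ 9 | n = 20, p = 0.50) = 74.8% in Cohort B. SAP 3.3 says about 80% for both. That gap is a separate matter; 76% and 75% are the no-loss reference values here.

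**Scan days.** 3 cycles × 21 days = 63 days, so scans fall on days 63, 126, 189 and 252, each ±7.

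**Trigger.** 365.25 / 2 = 182.6 days, taken as day 183.
- To the nominal third scan: 189 − 183 = 6 days.
- To the close of its window: 196 − 183 = 13 days.
- The window opens at 189 − 7 = day 182, so only a scan at its very start would be in the data.
- If follow-up ran from consent, up to 28 days before first dose, time since first dose could be only 183 − 28 = 155 days, about week 22.

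**Who is exposed, on scheduled scans with a cut at last first dose + 183 days**
- First response at week 9: confirmed by day 126 + 7 = 133. Safe.
- First response at week 18: confirmed by day 196. Exposed if first dosed within about 6 days (at most 13) of the last patient.
- First response at week 27: confirmed at day 252, or 259 at the latest. Exposed if first dosed within about 252 − 183 = 69 days (at most 76) of the last patient.
- Recent stopper: take a week-9 PR and a stop at week 11 (day 77). The previous scan is 77 − 63 = 14 days old, so no end-of-treatment scan is due. The patient meets the trigger at once, but the confirming scan is due on day 126.

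**Size.** Neither accrual time nor the timing of first response is in the documents, so this is an illustration. Assumptions: 20 patients per cohort accrued uniformly; cut at that cohort's own last first dose + 183 days; scans at 63k ± 7 days; no unscheduled scans; a responder counts only if the scan after first response is on or before the cut.

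| Scenario (12-month accrual, first response 70/20/10% at scans 1/2/3 unless stated) | Chance of rejecting |
|---|---|
| No loss | A 76%, B 75% |
| Cut at day 183 | A 69%, B 69% |
| Cohort A, accrual 6-18 months, patterns 80/15/5 to 60/25/15 | 58-73% |
| Cut at day 196, no hold for pending responses | about 72% in each |
| Cohort A, confirmatory scan 4 weeks after each first response | 73% |
| Cohort A closes 60 days before the study's last patient | about 75% |
| Cohort A closes 90 days before | 76% (no loss) |

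In the day-183 base case Cohort A loses 0.47 responders on average: 0.16 first seen at week 18 and 0.31 assumed to be first seen at week 27. A day-196 cut removes the week-18 loss entirely.

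**The case against.** - **Unscheduled scans.** A reader might infer that a late response cannot be confirmed, or that only week-9 responders can count at minimum follow-up. The documents do not support that. Unscheduled scans are allowed, and 4 weeks after a week-18 scan is day 126 + 28 = 154 (147-161 with the window), well before day 183. This stands. But nothing asks sites to do such a scan, so confirmation would depend on local habit.
- **Few patients are exposed.** Six months is a minimum that all patients must meet, so most will have more follow-up. This stands, and the week-18 problem alone is small. Any finite cut-off loses some late responses.
- **The trigger is study-wide.** The cohort that closes first gains follow-up, so the falls for A and B should not both be taken in full.
- **One stopper does not start the analysis.** All other patients must qualify too, and scanning continues meanwhile. If any still-treated patient was first dosed no more than 50 days before the stopper, the cut falls on or after the stopper's day 133 (183 − 50), and a week-9 PR can be confirmed. The gap is therefore limited to the end of enrolment, but the wording leaves it open.
- **Tumor flare.** A reader might add that the protocol expects responses after an initial flare, making late responses common. This does not bear on the primary endpoint. Appendix D describes flare as radiographic progression per RECIST 1.1, and primary ORR uses only evaluations before progression (Protocol 11.5.3.1). It matters only for the iRECIST endpoints.

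**Conclusion.** The misalignment is real and follows from the documents alone: the minimum follow-up ends about 6 days before the nominal third scan and 13 days before its window closes, an unconfirmed CR or PR is scored SD, and no rule waits for a pending confirmation. Stopping treatment also meets the trigger with a confirmation outstanding.

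The bias can only lower ORR, so it cannot create a false positive. In the base case it is under half a Cohort A responder on average and about 7 percentage points in the chance of rejecting (76% to 69%). About a third of that responder loss (0.16 of 0.47) comes from week-18 responses; the rest depends on the assumed share of first responses at week 27. It would be smaller in a cohort that closes earlier or if unscheduled scans are done. The direction is certain, but the size is not.

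A reader might conclude that a 37-week minimum (day 259) is needed because the model then returns to 76%. That result is built in, since the model allows no first response after the third scan. A 37-week floor for everyone is a debatable trade-off and is not required to correct the misalignment.

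**What to change.** Reword SAP 4.4 in three respects:

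1. Run the primary analysis once every treated patient has at least 28 weeks from first dose (day 196, when the third scan window closes), or has earlier had RECIST 1.1 progression, death, new anticancer therapy, withdrawal of consent or loss to follow-up. This also fixes when follow-up starts.
2. Delete stopping study treatment as a sufficient condition by itself.
3. Do not cut the data while any unconfirmed CR or PR has its next scheduled scan still due. Limit this to responses first seen by the date condition 1 is met, so that the wait is bounded.

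The third element also covers patients whose cycle-based scans run late because of dosing delays.

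Cost: 196 − 183 = 13 days, about 2 weeks. If a response is pending, add at most one scan interval, about 9-10 weeks (63 days, or 70 with the window). No new patients or scans are needed.

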5. STATISTICAL ANALYSIS

5.1. General Methods

All recorded data will be presented in listings.

The categorical data will be summarized using frequency counts and percentages of patients. The continuous data will be summarized using number of non-missing observation (n), mean, standard deviation, median, minimum and maximum unless otherwise specified.

Summary tables will be presented by cohort. Data listings will be presented with patient ID and cohort.

For concomitant medications/therapy and adverse events, the cycle number is determined based on their start/onset dates. For other collected data, the cycle number is determined based on their visit dates. These data include Lab test, Physical exam, Vital signs, Height and Weight, Ophthalmological exam, ECOG, ECG, Pregnancy test, Tumor biopsies, Scheduled tumor assessment.

When there are multiple laboratory records for a scheduled visit, the one closest to the target date will be used for analysis. If there are two or more records with the same time period to the target date, the record with the latest database entry date will be used for analysis.

Time to event distribution, PFS, OS, DoR, time to onset of adverse event of special interest (AESI) in a specific category, and time to resolution of AESI in a specific category, will be estimated using Kaplan–Meier techniques. The number of events and censorings will be reported. When appropriate, the median along with the corresponding log-log transformed 95% CI will be estimated. Rates at fixed time points will be derived from the Kaplan-Meier estimate and corresponding confidence interval will be derived based on Greenwood formula for variance derivation and on log-log transformation applied on the survivor function $S(t)$. Confidence intervals for binomial proportions, ORR and DCR, will be derived using the Clopper–Pearson method.

All the analyses of efficacy, safety, and pharmacodynamics data for this study will be performed using SAS® statistical software package, Version 9.3 or a higher version.

5.2. Study Conduct

5.2.1. Accrual

The number of patients accrued will be summarized by country and investigational site on All Enrolled Population. A by-patient listing of accrual with cohort, first dosing date, country and investigational site will also be presented.

5.2.2. Protocol Deviations

Important protocol deviation (ICH E3 Q&A (R1)) is defined as a subset of protocol deviations that may significantly impact the completeness, accuracy, and/or reliability of the study data or that may significantly affect the subject's rights, safety or well-being. These include: Important ICF issues, inclusion/exclusion criteria not met, withdrawal criteria not followed; wrong treatment, incorrect dose/overdose based on protocol definitions, important deviations based on protocol design, and other important GCP deviations.

Important protocol deviations will be summarized by category and listed as well.

According to the FDA's guidance on conduct of clinical trials of medical products during COVID-19 pandemic, updated on March 27, 2020 (FDA, 2020), and the EMA's guidance on the management of clinical trials during the COVID-19 (Coronavirus) pandemic, updated on April 28, 2020 (EMA, 2020), protocol deviations related to COVID-19 will be listed in the CSR.

5.3. Study Population

5.3.1. Patient Disposition

The number of patients in each study population (All Enrolled Population, All Treated Population, CCI [REDACTED]) will be summarized by cohort. Patient

disposition table will include number of patients treated at data cutoff, number of subjects with treatment ongoing at data cutoff, number of discontinued patients along with the reason for study discontinuation.

5.3.2. Demographic and Other Baseline Characteristics

The following baseline characteristics will be summarized by cohort. Listings will also be provided.

- Age
- Age category (< 65, ≥65)
- Sex (Male, Female)
- Ethnicity (Hispanic/Latino, Not Hispanic/Latino, Unknown)
- Race (American Indian/Alaska Native, Asian, Black/African American, Caucasian/White, Native Hawaiian/Other Pacific Islander, Other)
- Region (North America, Europe)
- ECOG PS (0, 1)
- Baseline height
- Baseline weight
- Location of Primary Tumor (Bladder, Upper Tract)
- Sub-type of Location of Primary Tumor (Basal-squamous, Luminal-papillary, Luminal-infiltrated, Luminal, Neuronal, Unknown)
- Any metastases (Yes, No)
- Prior surgery (Yes, No)
- Prior radiotherapy (Yes, No)
- Prior systemic anti-cancer therapy (Yes, No)
- Number of prior lines of systemic therapy
- *FGFR* Status

- *FGFR1* Fusion, Rearrangement, or Translocation (Yes, No)
- *FGFR2* Fusion, Rearrangement, or Translocation (Yes, No)
- *FGFR3* Fusion, Rearrangement, or Translocation (Yes, No)
- *FGFR3* mutation other than Fusion, Rearrangement, or Translocation (Yes, No)
- *FGFR4* Fusion, Rearrangement, or Translocation (Yes, No)

All collected information for cancer diagnosis will be summarized and listed.

